4.3.2 Justification of the model-based approach

An essential feature of the model is that it fits regression lines to profiles of CIMT values consisting of two pre-randomization values, three values from visits during the treatment period, and two end-of-study visits. In the event that a subject withdraws with an incomplete profile after the pre-randomization ultrasound visits, an advantage of this approach is that regression lines can still be fitted to the data available. This regression approach is appropriate because CIMT values (and therefore primary and secondary endpoints based on them) are expected to change in a linear fashion over time. Analysis of CIMT data and presentation of results as annualized progression or regression rates is conventional, see for example [Espeland 2005](#).

4.3.3 Details of the statistical models

The statistical model (i) reflects the multilevel repeated measures structure of the data, (ii) focuses on the time-profile of CIMT values, (iii) uses all available data by including subjects with incomplete data, and (iv) is consistent with pre-planned statistical analyses described in the protocol. Objectives for analysis are to estimate and test the statistical significance of the treatment effect (rosuvastatin compared with placebo). For time of CIMT measurement, the 2 pre-randomization visits and the final 2 visits at the end-of-study will be treated as separate time points.

The two pre-randomization CIMT scans, denoted by BL2 and BL3, are expected to be highly predictive of CIMT values post-randomization, and the way in which they are included in the statistical model is therefore important (Cnaan et al 1997). A model which has BL2 and BL3 as baseline covariates has greater flexibility in allowing a difference between changes from baseline to the first post-randomization assessment of CIMT (six months) and change from six months on, however the disadvantage is that only change from 6 months to two years is estimated by the model. For this reason, a model which has BL2 and BL3 as part of the response profile is preferred because BL2 and BL3 then contribute to estimation of regression lines at the subject-site level. Furthermore, this model reflects what is believed (and supported by the results in the global Meteor study) to be the behavior of CIMT over time, in other words changes over the 2-year treatment period in both treatment groups are expected to be small and smoothly continuous with time. Further advantages are that terms in the model (Time and Time x Treatment) estimate changes over the entire treatment period from baseline up to 2 years, and all estimates of effects and p-values for the between-group comparisons can be obtained from a single model by comparing and testing slopes and interactions.

Random effects in the model will consist of subject intercepts and slopes. Thus, random effects in the model allow subjects to have different intercepts and slopes. The model assumes the treatment-time effect will be the same for all carotid sites. This is consistent with the expected effect of rosuvastatin or placebo on carotid artery sites.

An unstructured covariance matrix is used by default to give maximum flexibility in model fitting. If the unstructured covariance matrix results in a lack of convergence, alternative covariance structures, i.e., compound symmetry, will be used.

The adequacy of the basic model will be assessed by including additional terms for time-squared and time-squared by treatment interaction. This is to explore non-linearity in the effect of time. These terms will be assessed using likelihood ratio tests comparing models fitted by maximum likelihood. The additional terms will not be included in the final model if they are not statistically significant at the 0.05 level.

Consistency of the treatment effect in individual carotid artery sites will be demonstrated by means of summary statistics for CIMT values at each visit for each treatment group.

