#### **3.1 Inclusion criteria**

For inclusion in the study, subjects should fulfill the following criteria:

1. Provision of informed consent prior to any study-specific procedures
2. Male aged  $\geq 45$  and  $< 70$  years or female aged  $\geq 55$  and  $< 70$  years
3. Subjects with only hypertension (as defined blood pressure  $\geq 140/90$  mmHg or on antihypertensive treatment) and age as CVD risk factors and subjects without hypertension who have 3 or more other risk factors (including age) must have:
  - Fasting LDL C of  $\geq 120$  mg/dL (3.1 mmol/L) and  $< 160$  mg/dL (4.1 mmol/L)Subjects without hypertension who have fewer than 3 other risk factors (including age) must have:
  - Fasting LDL-C of  $\geq 120$  mg/dL (3.1 mmol/L) and  $< 190$  mg/dL (4.9 mmol/L)
4. Triglycerides  $< 500$  mg/dL (5.65 mmol/L) at Visit 1 (Week -6)
5. HDL-C levels  $\leq 60$  mg/dL (1.6 mmol/L) at Visit 1 (Week -6)
6. Maximum IMT  $\geq 1.2$  mm and  $< 3.5$  mm at any location in the carotid ultrasound scans conducted at both Visit 2 (Week -4) and Visit 3 (Week -2)
7. Willing to follow all study procedures including study visits, fasting blood draws, and compliance with study treatment regimen

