#### **8.5.1 Analysis of the primary efficacy variable**

A linear mixed-effects model will be used for the primary analysis to assess the difference in the annualized rate of change in the CIMT measurements across 12 carotid artery sites between rosuvastatin 20 mg and placebo treatment over 104 weeks.

For the primary efficacy analysis, the dependent variable is the maximum CIMT measurement from 3 interrogation angles at each of the 12 carotid artery sites at each timepoint of CIMT measurement during the 104-week study period. The model includes fixed effects for treatment group, time, time by treatment interaction, ICVD risk stratification (<5%/5% to 10%), age, sex, centre and scan reader, and random effects for the intercept and slope at the individual subject level and carotid artery site within subject. Ultrasound machine will be included as a fixed effect as well if different types of machines are deployed across sites. For time of CIMT measurement, the 2 pre-randomization visits and the final 2 visits at the end-of-study will be treated as separate time points. Details will be defined in the Statistical Analysis Plan. Time, as a continuous variable, is the interval from the date of randomization to the date of CIMT measurement. Differences in annualized change between rosuvastatin and placebo will be evaluated by testing the time-by-treatment interaction term.

In the analysis, let  $\beta_1$  and  $\beta_2$  represent respectively the coefficient parameters for time and time by treatment interaction in the mixed effect model. The annualized rate of change (slope) in MeanMax CIMT in placebo will be estimated by the coefficient parameter  $\beta_1$ , the annualized rate of change (slope) in MeanMax CIMT in rosuvastatin will be estimated by  $\beta_1 + \beta_2$ , and the difference of annualized rate (slope) of change between 2 groups will be estimated by  $\beta_2$ . Then, the null and the alternative primary hypothesis can be expressed as  $H_0: \beta_2 = 0$  vs.  $H_a: \beta_2 \neq 0$  at a significance level of 0.05 two-sided.

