The two IMT measurements taken before randomization must meet inclusion criteria of maximum IMT ≥ 1.2 mm and < 3.5 mm. The final two IMT procedures should be performed on different days when possible. The second of the final IMT procedures should occur at or before week 104, at the time of discontinuation of study treatment.

Batch reading of all the 7 scans (2 before and 5 after randomization) of a given subject will be done by the same reader over a short period of time for each randomized and treated subject upon completion of (or premature discontinuation from) the 2-year treatment. This will reduce the influence of between reader variability and temporal drift in measurements. Only batch-read CIMT data will be used for statistical analysis of efficacy because of its greater accuracy. However, for randomized subjects who did not receive study medication with no post-randomisation scans, if the two scans before randomization are not be batch read, the eligibility CIMT reading data will be used instead for statistical analysis of efficacy. For randomized subjects who did receive study medication with no post-baseline scans, the same approach will apply.

Since the subjects may miss visits or prematurely withdraw before 2 years, we may have incomplete efficacy observations. Also, IMT measurement from ultrasound scan may occasionally be immeasurable at all 3 angles for some carotid sites.

Following is a summary diagram describing the CIMT measure, data derivation, and data analysis process in terms of dependent variable and summary statistics.

Figure 2 Summary for CIMT endpoints

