4. ANALYSIS METHODS

4.1 General principles

All statistical evaluation, as well as summaries and tabulations will be done by qualified personnel at IQVIA. Before breaking the treatment codes, following clean file declaration, all decisions made on the evaluability of the data for each individual subject will be documented and each subject will be assigned to the appropriate analysis data set.

The primary analysis for efficacy variables will be based on the ITT analysis set. The CIMT analysis will be performed on the PP population as a robustness check of the analysis on ITT analysis set.

A multilevel, repeated measures, linear mixed effects model will be used for the analysis of the primary and secondary CIMT end points. Rationale for the choice of the model follows Espeland et al (1992 and 1999) and Pitt et al (2000). Details of the model are given in section 4.3.3.

No multiplicity adjustment will be applied to the secondary efficacy analysis.

Lipid and Apo analyses will be performed on the ITT analysis set only. The definition of baseline for laboratory endpoint variables is given in section 4.1.1.

Secondary lipid and lipoproteins outcome measures are the percentage change from baseline, which will be analyzed by analysis of covariance (ANCOVA) with terms for treatment as a factor and baseline value as a covariate in the model. For lipid measurements (LDL-C, total cholesterol, HDL-C, TG, non-HDL-C, non-HDL-C/HDL-C), both the analysis of the percent change from baseline at final visit, and the analysis of the percent change from baseline to time-weighted average during treatment will be performed. In the evaluation of change from baseline to final visit, missing observations will be imputed by last observation carried forward (LOCF) method. No imputation will be made for missing lipid values for time-weighted average analysis.

During the study, LDL-C measurement was transitioned from 2nd generation reagent to 3rd generation reagent by direct assay. Post-baseline LDL-C values will be affected. To evaluate the consistency of different measurement reagents, all post-baseline LDL-C related analysis will be performed on two sets of data.

- LDL-C values as collected, regardless of the type of reagent.

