4.3 Efficacy analysis

CIMT Data

In this study the CIMT data has a hierarchical (or multilevel) structure. The levels for the data are defined by 1) the study participants and 2) carotid artery sites within the participants. The repeated measure is time.

A multi-level, linear mixed-effects model will be used for the primary analysis to assess the difference in the annualized rate of change in the CIMT measurements across 12 carotid artery sites between rosuvastatin 20 mg and placebo treatment over 104 weeks. The model is specified in terms of fixed effects for randomized treatment group, time, time by treatment interaction, ICVD risk stratification (<5%/5%-10%) – based on IxRS data, carotid artery site,

age, sex, centre, and scan reader (In the unlikely event that the model does not converge it may be necessary to drop fixed effects for reader, sex and age in that order). Random effects within the model are the intercept and slope for individual subjects. Time in the model is a continuous measure and is the interval in years from date of randomization to date of CIMT measurement and its effect is linear.

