Appendix C SAS codes for statistical models used in the efficacy analysis.

Multi-level linear mixed effects model for primary efficacy analysis:

```
PROC MIXED;
CLASS TRT SITE SUBJID ICVD SEX READER CENTRE;
MODEL RESPONSE = TRT TIME TRT*TIME ICVD SITE CENTRE AGE SEX READER
/ SOLUTION DDFM = KR CL COVB;
RANDOM INTERCEPT TIME /SUB = SUBJID TYPE = UN;
RUN;
```

Note: The maxCIMT value for each site will be the dependent variable (RESPONSE) in the mixed effects model. Time is a continuous variable per the protocol and will be the interval in years from date of randomization to date of the CIMT measurement. The fixed effect Time in the MODEL statement is not declared as a class variable; thus it models a linear trend in time. We want to see the change in slope over time for the difference between rosuvastatin and placebo across all sites.

The TYPE=UN option in the RANDOM statement specifies an unstructured covariance matrix for the random intercept and slope effects at the individual subject level.

[figure not shown]
ANCOVA analyses for the laboratory efficacy endpoints:

[figure not shown]
```
PROC GLM;  
CLASS TRT;  
MODEL PER_CHG = TRT BASE /CLPARM;  
LSMEANS TRT / STDERR PDIFF CL;  
ESTIMATE 'ROSUVASTATIN 20 MG VS PLACEBO' TRT 1 -1/CL;  
RUN;
```

PER_CHG = Percentage change from baseline
TRT = Randomized treatment
BASE = Baseline value

[figure not shown]

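### The SAP's primary CIMT model drops the carotid-site-within-subject random effects in the protocol, which can inflate the standard error and cost power

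*SAP*

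**What the plan says.** Protocol 8.5.1 (and the synopsis) lists "random effects for the intercept and slope at the individual subject level and carotid artery site within subject". SAP 4.1 announces a model of the same kind: "A multilevel, repeated measures, linear mixed effects model will be used for the analysis of the primary and secondary CIMT end points". SAP 4.3 describes the nesting: "The levels for the data are defined by 1) the study participants and 2) carotid artery sites within the participants".

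The model then specified has one random level. SAP 4.3.3 says "Random effects in the model will consist of subject intercepts and slopes", SAP 4.3 says the same, and Appendix C codes "RANDOM INTERCEPT TIME /SUB = SUBJID TYPE = UN". Carotid site enters only as a fixed effect, and there is no REPEATED statement.

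SAP 4.3.3 nevertheless describes the model as consistent with the protocol. It justifies keeping the two pre-randomization scans in the response because "BL2 and BL3 then contribute to estimation of regression lines at the subject-site level". The coded model has no lines at that level.

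**The concern.** The fixed SITE effect removes the 12 average site levels and nothing more. If one subject's left bulb far wall is always thick, all seven of its readings sit above that subject's line together. The SAP model treats those seven deviations as independent noise.

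Two consequences follow.

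- **Complete data.** The slope estimate is unaffected, but its reported standard error can be too large.
- **Missing readings.** SAP 3.1 accepts that "IMT measurement from ultrasound scan may occasionally be immeasurable at all 3 angles for some carotid sites". When sites come and go between scans, site level leaks into the slope, and real precision is lost as well.

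At stake is power for the primary test and for the four secondary CIMT endpoints, which reuse the model on four sites each.

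**Working it through.** **Inputs.** Seven scans (SAP 3.1), placed at weeks -4, -2, 26, 52, 78, 103 and 104; week 103 is assumed for the first of the final pair. N = 506 planned and 543 randomized (synopsis), allocated 1:1. METEOR difference -0.0145 mm/year, 95% CI -0.0196 to -0.0093, arms of 702 and 282 (Protocol 1.1). The plan's own sample size cannot be reproduced: Protocol 8.2 and Appendix H, and SAP 1.3 and Appendix D, are redacted. Residual SD σ = 0.15 mm is assumed.

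**1. Total slope SD.** METEOR SE = 0.0103/3.92 = 0.00263. Slope SD = 0.00263/√(1/702 + 1/282) = 0.0373 mm/year.

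**2. Spread of scan times.** With time in years, the sum of squares is 4.70 per site, so Sxx = 56.4 for 12 sites and 18.8 for 4.

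**3. Subject slope variance τ².** The correct per-subject slope variance is τ² + σ²/Sxx = 0.0373² = 0.001391. Since 0.0225/56.4 = 0.000399, τ² = 0.000992 and τ = 0.0315.

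**4. When the SAP model goes wrong.** Each subject has 84 readings, leaving 82 degrees of freedom after the subject's own line; site levels account for 11 × 7 = 77 of them. With site-within-subject SD φ, the fitted residual variance is about σ² + (77/82)φ². The subject slope variance shrinks to compensate, and the total stays correct until it reaches its boundary. That happens at φ/τ = √(56.4 × 82/77) = 7.7, or φ = 0.244 mm. For four sites it happens at √(18.8 × 26/21) = 4.8.

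**5. Size beyond that point.** With fitted slope variance zero, the residual variance is about s² = (77φ² + 83σ² + Sxx·τ²)/83, and the SE ratio is √(s²/Sxx)/0.0373.

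- φ = 0.30: s² = (6.93 + 1.87 + 0.06)/83 = 0.1067; ratio 0.0435/0.0373 = 1.17.
- φ = 0.40: s² = (12.32 + 1.87 + 0.06)/83 = 0.172; ratio 0.0552/0.0373 = 1.48.

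A large-sample likelihood fit of the SAP's unstructured matrix retains a little slope variance at the boundary and gives 1.18 and 1.49. Ratios from that fit, accurate to about 0.01:

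| Total slope SD (mm/year) | φ = 0.20 | 0.25 | 0.30 | 0.40 |
|---|---|---|---|---|
| 0.0373 | 1.00 | 1.03 | 1.18 | 1.49 |
| 0.045 | 1.00 | 1.00 | 1.00 | 1.24 |
| 0.050 | 1.00 | 1.00 | 1.00 | 1.13 |

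Four-site endpoints, at an assumed total slope SD of 0.045 to 0.050: 1.09 to 1.20 at φ = 0.20, and 1.42 to 1.57 at 0.30.

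**6. Power, complete data.** SE = 0.0373 × √(4/506) = 0.00332. The estimate is unchanged and only its reported SE grows by the ratio r, so power = Φ(d/SE - 1.96r).

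| Effect d, N | r = 1.00 | r = 1.18 | r = 1.49 |
|---|---|---|---|
| 0.0145, 506 | 99% | 98% | 93% |
| 0.0145, 543 | 99% | 99% | 95% |
| 0.010 (assumed), 506 | 85% | 76% | 54% |

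Type I error = 2[1 - Φ(1.96r)]: 5%, 2.1% and 0.4%.

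**7. Missing readings.** With 15% of site readings missing at random (assumed) and slope SD 0.0373, the ratio is 1.03, 1.24 and 1.56 at φ = 0.20, 0.30 and 0.40. Of this, 3 to 13% is real loss of precision. Power at 0.0145 and N = 506 is 95% at φ = 0.30 and 86% at 0.40.

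**8. Simulation.** REML fits at N = 506 and φ = 0.40 gave SE ratios of 1.48 (complete, 137 trials) and 1.56 (15% missing, 109 trials), with type I error below 1% and power 90% and 84% at 0.0145. With other assumed components (φ 0.4, residual SD 0.2, subject slope SD 0.02, site slope SD 0.03, 20% missing sites, 25% dropout), power was 0.67 against 0.98 with the site terms included. A milder set (0.15, 0.15, 0.03, 0.06, 15%, 20%) showed no loss: 0.97 against 0.96.

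**9. Is φ of this order plausible?** Protocol 3.1 needs a maximum IMT of at least 1.2 mm at one location only. One site standing D above the other 11 gives a within-subject site SD of D/√12: D = 0.7 mm gives 0.20 and D = 1.4 mm gives 0.40.

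**The case against.** - **The protocol sentence is loose.** It could mean site intercepts and slopes, or only a site-within-subject effect. Either reading includes a level that the SAP lacks.
- **The change may be deliberate and declared.** The SAP adds a fixed site effect that the protocol does not list, and SAP section 6 is redacted. This stands: no undeclared change can be alleged. A declaration would not restore the level or reconcile 4.3, 4.3.3 and Appendix C.
- **The harm is conditional.** Many cells are 1.00, and at METEOR's effect the complete-data loss is small. The fall from 85% to 54% needs an effect of 0.010 mm/year, which is not in the documents. This also stands. The trial does use 20 mg against METEOR's 40 mg (Protocol 1.2), so a smaller effect cannot be excluded.
- **The components are assumed.** D = 0.7 mm already puts the other sites at 0.5 mm when the maximum is 1.2 mm, and gives an SD at which complete-data inflation is nil. The threshold of 0.244 mm moves to 0.20 with residual SD 0.20 and to 0.27 with 0.10. Fair, and the reason only ranges are given.
- **Missingness may be rare or persistent.** A site never measurable in a subject leaks nothing into the slope; only intermittent gaps do. The 15% is an assumption.
- **SAP 4.3.6 fits each subject's slope with that subject's own site terms.** True, but that output is descriptive and does not test treatment.

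**Conclusion.** The discrepancy is plain in the text, and the model as coded does not have the structure that the SAP attributes to it. The effect on the primary test runs from nothing to a standard error about 1.5 times too large with complete data, depending on variance components that the public documents withhold. At METEOR's effect and 506 subjects, power falls from 99% to between 93% and 98% with complete data at site SD 0.40 to 0.30 mm, and further with intermittent gaps. The four-site secondary endpoints reach the problem at smaller site variance.

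No scenario showed false-positive inflation. That conclusion assumes the subject random slope stays in the model with its unstructured matrix; the compound-symmetry fallback in SAP 4.3.3 was not examined. The other assumptions are that METEOR's slope SD carries over and that the residual SD is near 0.15 mm. This should be corrected before unblinding, but it does not threaten the validity of a positive result.

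**What to change.** Before unblinding, restore the second level in SAP 4.3, 4.3.3 and Appendix C:

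- Keep the subject-level RANDOM statement and add `RANDOM INTERCEPT TIME / SUB=SITE(SUBJID);`. State its covariance type; the SAS default, variance components, is acceptable.
- Replace the sentence in 4.3.3 with: Random effects consist of intercepts and slopes for subjects and for carotid artery sites within subjects.
- State in advance that the site level reduces to an intercept only if the model does not converge. Place this step in order against the existing fallbacks (dropping reader, sex and age in 4.3; compound symmetry in 4.3.3).
- Use the same structure for the four secondary CIMT endpoints.

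The cost is one extra statement, longer run time and some convergence risk, which the stated reduction handles. No new data are needed.

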#### **Study site(s) and number of subjects planned**

Approximately 506 Chinese subjects will be randomized to study treatment. The study will be conducted across approximately 30 sites in China.

543 Chinese subjects were randomized into study when the recruitment was completed, these randomized patients were from 25 sites in China.

---

Study period		Phase of development
Estimated date of first subject enrolled	3Q 2015	Phase 3
Estimated date of last subject completed	1Q 2019	Phase 3

---

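### The compound-symmetry fallback for the primary model forces the intercept and slope variances to be equal; if it is used, the standard error of the primary comparison is too large.

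*SAP*

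**What the plan says.** - SAP 4.3.3 takes an unstructured covariance matrix as the default and adds: "If the unstructured covariance matrix results in a lack of convergence, alternative covariance structures, i.e., compound symmetry, will be used". No other structure is named.
- The same section states: "Random effects in the model will consist of subject intercepts and slopes".
- Appendix C codes this as "RANDOM INTERCEPT TIME /SUB = SUBJID TYPE = UN" and explains that the option "specifies an unstructured covariance matrix for the random intercept and slope effects at the individual subject level". There is no REPEATED statement, so the residuals are independent with one variance.
- SAP 4.3 measures time in years and has its own response to non-convergence, which it calls unlikely: "it may be necessary to drop fixed effects for reader, sex and age in that order". Neither section says which rule comes first.
- Protocol 8.5.1 describes a richer model, with "random effects for the intercept and slope at the individual subject level and carotid artery site within subject". The site-within-subject random effect is absent from the SAP text and from the code. SAP section 6 (changes from protocol) is redacted, so whether this was declared cannot be seen.

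**The concern.** The only matrix in the code that carries TYPE=UN is the 2×2 intercept-slope matrix. Compound symmetry gives it a single common diagonal element. One diagonal entry is in mm² and the other in (mm/year)², so the equality has no meaning: recording time in months would change the constraint and the p-value.

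The primary test is the time-by-treatment interaction, and its standard error depends directly on the slope variance. If subjects vary more in wall thickness than in yearly progression, the common value lies well above the true slope variance. The interaction is then tested against a standard error that is too large, and a real effect can be missed.

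The missing site-within-subject effect bears on how the fallback might be reached. Without it, site variance enters the residual and pushes the estimated slope variance toward zero. The SAP does not say whether such a boundary fit counts as lack of convergence, so two analysts could report different primary p-values from the same data.

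**Working it through.** **No figure of the plan to reproduce.** The documents show no standard error, variance component or power for the primary model, and the sample-size assumptions are redacted. The inputs below are therefore partly assumed.

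**Inputs from the documents.** N = 543 randomized (Protocol synopsis: "543 Chinese subjects were randomized into study when the recruitment was completed"), with 506 planned; 1:1 allocation; two-sided 5% test; 12 sites and 7 scans. The earlier global study (Protocol 1.1) gives a difference of −0.0145 mm/year, 95% CI −0.0196 to −0.0093, with arms of 702 and 282.

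**Assumed.** Measurement SD 0.15 mm; site-within-subject SD 0–0.35 mm; intercept SD 0.05–0.20 mm; complete data; final two scans at weeks 103 and 104.

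**Slope SD.**
- SE in the earlier study = (0.0196 − 0.0093)/(2 × 1.96) = 0.00263.
- Effective slope SD = 0.00263/√(1/702 + 1/282) = 0.0373 mm/year.
- The sum of squares of time over 12 × 7 readings is 56.4.
- True slope SD = √(0.0373² − 0.15²/56.4) = 0.0315; 0.0314 is used.

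**One case by hand** (intercept SD 0.10, site SD 0). With complete data, variance of the slope difference = (4/N) × (slope variance + 0.15²/56.4).
- True SE = √[(4/543)(0.000986 + 0.000399)] = 0.00319.
- With negligible error, the compound-symmetry variance is the average of the two true variances: (0.0100 + 0.000986)/2 = 0.00549.
- Model SE = √[(4/543)(0.00549 + 0.000399)] = 0.00659, a ratio of 2.06.
- Power = Φ[(0.0145 − 1.96 × 0.00659)/0.00319] = Φ(0.50), about 69%. With the true SE it is Φ(0.0145/0.00319 − 1.96), about 99.5%.

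**Full large-sample fits** (Appendix C model, expected log-likelihood optimised; ranges over site SD 0–0.35 mm):

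| Intercept SD (mm) | Model SE / true SE, CS | CS power, N=543 | CS power, N=506 |
|---|---|---|---|
| 0.05 | 1.2–2.0 | 76–98% | 71–98% |
| 0.08 | 1.7–2.3 | 53–89% | 47–86% |
| 0.10 | 2.0–2.5 | 33–71% | 27–66% |
| 0.15 | 2.9–3.3 | 3–11% | 2–9% |
| 0.20 | 3.9–4.1 | 0.1% or less | about 0.1% or less |

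Unstructured (UN) and uncorrelated (VC) fits give SE ratios of 1.0–1.34 and power of 97–99.5% (96–99% at N=506). The hand case agrees with the fitted 2.03 and 71%. An intercept-slope correlation of ±0.5 moves CS power by less than 1 point. Also varying slope SD over 0.020–0.037 and measurement SD over 0.10–0.20 (N=543), CS power in the order of the rows is 66–100%, 48–99%, 32–87%, 0.2–15% and under 1%, against 92–100%. At intercept SD 0.03 mm, close to the slope SD, CS power is 84–99.5%.

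**When the unstructured fit reaches its boundary.** With site variance in the residual, the residual variance tends to 0.15² + (77/82) × site variance. The estimated slope variance becomes slope variance − (77/82) × site variance/56.4, which is zero at site SD = slope SD × √(56.4 × 82/77) = 7.75 × slope SD. That is 0.155, 0.243 and 0.289 mm for slope SD 0.020, 0.0314 and 0.0373.

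**Simulation at the boundary** (REML, N=543, 300 trials in each of 32 cells). At slope SD 0.0314 the unstructured fit was on its boundary in at most 0.3% of trials at site SD 0.15–0.20, in 81–98% at 0.25 and in all at 0.35. CS power in the boundary trials, at intercept SD 0.05, 0.08, 0.10 and 0.15:
- site SD 0.25: 90, 76, 45 and 7%
- site SD 0.35: 73, 56, 34 and 2%

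VC and the bounded unstructured fit kept 97–100%.

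**Check with incomplete data.** A separate small simulation used 506 subjects, 20% dropout, 10% missing sites, intercept SD 0.20 and slope SD 0.03, with 60 replicates. The mean CS standard error was 0.0140 against an empirical SD of 0.0036. An effect of 0.0145 was detected in 98% of unstructured fits and in none of the CS fits.

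**The case against.** **The fallback may never be used.** SAP 4.3 calls non-convergence unlikely, and a zero variance estimate is ordinarily a converged fit. This stands: the size is conditional and the frequency unknown. But the SAP leaves the boundary case open, and a pre-specified fallback should give a valid test when it is called on.

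**The range covers settings where the boundary does not arise, and the unstructured fit is itself conservative.** Fair on the standard errors: at intercept SD 0.05 and site SD 0.35, CS is 1.95 and unstructured 1.34, so the fallback adds a factor of about 1.46 (1.95/1.34). The power comparisons are made directly against the alternatives, and the simulation isolates the boundary trials; the loss remains.

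**The key inputs are assumed.** True. Intercept SD drives the result and appears nowhere in the documents. The harm is small only when it is close to the slope SD, which is hard to credit when eligibility admits a maximum IMT from 1.2 to below 3.5 mm.

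**Compound symmetry might mean equal correlation among a subject's readings.** That is a random-intercept model, and it errs the other way: the standard error is about 0.55 of its true value at site SD 0 (type I error about 28%) and 0.88 at 0.20 (about 8%). Appendix C does not support this reading, and it would drop the random slopes required by 4.3.3. Type I error exceeds 5% only where site variation is low, and there the unstructured fit is unlikely to fail.

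**A VC fit with zero slope variance is also a random-intercept model.** Correct. It arises at site SD 0.25–0.35, where its standard error is 1.02–1.32 times the true value, so not too small.

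**Conclusion.** The concern holds. As Appendix C is written, the named fallback equates two variances in different units; that follows from the code and needs no assumption. If it is used and subject levels vary more than slopes, the primary standard error is 1.2 to 4.1 times its true value in the base case, and power for 0.0145 mm/year can fall from 97% or more to almost nothing. The numerical size rests on the assumed intercept, site and measurement SDs, on a slope SD taken from the earlier study, and on complete data. Under the Appendix C reading the error costs power and does not create false positives. It should be corrected, because the same model also serves the segment endpoints and the per-protocol analyses.

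**What to change.** Delete compound symmetry and replace the rules in SAP 4.3 and 4.3.3 with one ordered rule:

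1. Refit with new starting values, or with TYPE=FA0(2), the Cholesky form of the same unstructured matrix.
2. If that fails, use TYPE=VC: separate, uncorrelated intercept and slope variances.
3. Only then drop reader, sex and age, in the order already given.

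State that a VC slope variance estimated as zero is accepted and reported as such, and report which step was used.

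The cost is two sentences in the SAP and no new data. The downside is that VC assumes no intercept-slope correlation. If the true correlation is ±0.5, type I error is 0.029–0.075 at site SD 0–0.15 and at most 0.046 at site SD 0.25–0.35, where the unstructured fit is near or on its boundary (intercept SD 0.05–0.15, slope SD 0.020–0.0314, measurement SD 0.15). This change does not settle the missing site-within-subject effect, which needs its own reconciliation with Protocol 8.5.1.
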